Duration of administration	
Ibrutinib: ongoing (indefinite), with re-assessment of patient tolerance and response at 6 weeks, 3 months and 6 months
 
Rituximab: weekly x4, with or without a repeat 8 weeks after the initial therapy, depending on the patient's initial clinical response

Reference therapy	
Patients may have received steroids or other alternative GVHD regimens (with no new therapy for at least two weeks prior to the start of this protocol), without benefit,
 
OR
 
Patients may have shown an initial steroid benefit, but demonstrate an inability to undergo steroid taper due to persistent GVHD upon attempted steroid dose reduction.

Statistical Methodology	
GVHD response rates at 6 weeks, 3 months and 6 months will be assessed using exact binomial methods combining the initial dose escalation and expansion cohorts.
 
Univariate and multivariate analyses will be used to identify independent correlates of both safety and efficacy.

-------------------------	--------------------------------------------------------------------------------------------------------------------------------------------------------------------------------------------------------------------------------------------------------------------------------------------------

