## 7 Statistical Plan

## 7.1 Statistical Methods

GVHD response rates based on the GVHD Global Severity Score and Clinical Assessment ( Attachment 1) at 6 weeks, 3 months and 6 months will be assessed using exact binomial methods combining the initial dose escalation and expansion cohorts. With the expansion cohort after the safety dose escalation phase, a total of 15 patients will be available for evaluation. An exact test for proportions with a null hypothesis of a 15% response rate, an alternative hypothesis of a 50% response rate, and a one-sided significance level of 0.10, would have a power of 85% using 15 subjects, including a Bonferroni correction for looking at the 6 week, 3 month and 6 month response rates. This test rejects the null hypothesis if 6 out of 15 subjects respond. If only the 10 subjects from the expansion cohort are used, the null is rejected if 4 out of 10 respond, and the power is reduced to 0.83. Calculations were done in the PASS 2008 package.

Two-sample t-tests for continuous data and Fisher's exact test for binary data will be used to compare responders and non-responders for the purpose of identifying independent *biomarker* correlates of treatment response. The power and precision of these comparisons will depend on the number of responders and non-responders compared.

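### Section 7.1 adds an expansion-only rejection rule (4 of 10) that has no stated status and exceeds the plan's own Bonferroni level, beside the planned 6 of 15 test

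*Combined protocol and SAP*

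**What the plan says.** The Study Summary (Statistical Methodology) says of the response rates at the three assessment times (6 weeks, 3 months and 6 months) that they "will be assessed using exact binomial methods combining the initial dose escalation and expansion cohorts". The first sentence of section 7.1 makes the same commitment. Section 7.2 treats every subject who stays on study for at least 6 weeks as evaluable for efficacy and does not separate the cohorts.

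Section 7.1 sets up the test as follows: "An exact test for proportions with a null hypothesis of a 15% response rate, an alternative hypothesis of a 50% response rate". The error level is "a one-sided significance level of 0.10", and power is calculated "including a Bonferroni correction for looking at the 6 week, 3 month and 6 month response rates". For the combined set, the test "would have a power of 85% using 15 subjects", and the cut-off is given as follows: "This test rejects the null hypothesis if 6 out of 15 subjects respond".

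The next sentence gives a second rule for the same null: "If only the 10 subjects from the expansion cohort are used, the null is rejected if 4 out of 10 respond". The power attached to it is 0.83. Nothing in the document says when the expansion cohort would be used alone, whether that result is supportive, or which result governs if the two differ. The Bonferroni correction is described for the three time points only.

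**The concern.** Two rejection rules for one null hypothesis, on nested sets of subjects, raise two questions.

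The first is whether each rule respects the error level that section 7.1 sets. If the 4 of 10 rule does not, a claim of efficacy based on it would carry more than the stated one-sided 0.10 risk, and the 0.83 beside it would make the expansion-only test look almost as strong as the combined one.

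The second is whether the plan excludes choosing the set after responses are known. The trial is open label with a single arm, so responses are visible as they accrue. The cohorts also differ in how ibrutinib is started: the first five subjects begin at 140 mg and escalate, while the expansion cohort begins at 420 mg or a reduced level set by the escalation results (section 5.1.1). A reason to report the expansion cohort alone would be easy to find afterwards.

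**Working it through.** **Inputs, all from section 7.1.** Null rate 0.15; alternative rate 0.50; one-sided alpha 0.10; Bonferroni over three time points, so 0.10/3 = 0.0333 per test; cut-offs 6 of 15 and 4 of 10; stated powers 85% and 0.83.

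**Step 1. Reproduce the stated powers.** For X ~ Bin(n, p), the rejection probability is P(X ≥ r). Type I error takes p = 0.15 and power takes p = 0.50.

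| Rule | Type I error | Power | Within 0.0333? |
|---|---|---|---|
| 5 of 15 | 0.0617 | 0.941 | no |
| 6 of 15 (plan) | 0.0168 | 0.849 | yes |
| 3 of 10 | 0.1798 | 0.945 | no |
| 4 of 10 (plan) | 0.0500 | 0.828 | no |
| 5 of 10 | 0.0099 | 0.623 | yes |

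Both stated powers reproduce (0.849 and 0.828).

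**Step 2. Compare the cut-offs with the stated level.** At 0.0333 the smallest allowed cut-off on 15 subjects is 6, because 5 gives 0.0617. On 10 subjects it is 5, because 4 gives 0.0500. The 4 of 10 rule is the smallest cut-off at an uncorrected 0.10, because 3 gives 0.1798. So the combined rule carries the Bonferroni correction and the expansion rule does not. The fall in power from 85% to 83% compares unlike tests; with both corrected, power falls from 0.849 to 0.623.

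**Step 3. Error if either rule may be used.** Let X ~ Bin(10, 0.15) be expansion responders and Y ~ Bin(5, 0.15) escalation responders, independent and with the same rate. Reject if X ≥ 4 or X + Y ≥ 6.

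- Both rules reject: 0.0127
- Expansion rule only: 0.0373, from (X, Y) = (4,0), (4,1), (5,0)
- Combined rule only: 0.0041, from (1,5), (2,4), (2,5), (3,3), (3,4), (3,5)
- Either: 0.0127 + 0.0373 + 0.0041 = 0.0541

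Of this 0.0541, the 4 of 10 rule alone supplies 0.0500. With a 5 of 10 cut-off, the only expansion-only outcome is (5,0), with probability 0.0038, so either rule gives 0.0168 + 0.0038 = 0.0206, below 0.0333.

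**Step 4. Three time points.** The bound is three times the per-visit rate. If the visits were independent, the rate is 1 − (1 − a)³. If a subject's response were identical at all three visits, the rate is a.

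| Used for rejection | Identical visits | Independent visits | Bound |
|---|---|---|---|
| 6 of 15 only | 0.017 | 0.050 | 0.050 |
| 4 of 10 only | 0.050 | 0.143 | 0.150 |
| Either (4 of 10) | 0.054 | 0.154 | 0.162 |
| Either (5 of 10) | 0.021 | 0.060 | 0.062 |

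Simulation of the either-rule case (100,000 trials, a Gaussian latent variable per subject) gives 0.125 at a between-visit correlation of about 0.45, 0.105 at about 0.67 and 0.062 at about 0.97.

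**Step 5. How often the rules disagree at one time point.** With 4 of 10, the probability that exactly one rule rejects is 0.041, 0.174 and 0.113 at true rates of 15%, 30% and 50%. With 5 of 10 it is 0.014, 0.163 and 0.241. For example, 4 of 10 plus 1 of 5 rejects on the expansion set, while 5 of 15 does not reject. In reverse, 3 of 10 plus 3 of 5 rejects at 6 of 15 only.

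**The case against.** A reader might infer that the plan has no rule for which test decides, and so returns two opposite answers on one dataset. The documents do not support that. The Study Summary and the opening of section 7.1 both commit to the combined cohorts, and section 7.2 does not divide subjects by cohort. Followed as written, 6 of 15 decides. The expansion-only sentence can also be read as a design-stage remark on power: it is conditional, it ends with a power figure, and it sits just before the software note. That reading is fair. But the sentence is worded as a rejection rule, and nothing marks it as supportive or says when it applies.

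A reader might also infer that the freedom to choose between sets is what breaks the 0.10 level. Step 3 shows otherwise: adding the combined rule to the 4 of 10 rule raises the per-visit error only from 0.0500 to 0.0541, and with a correctly set 5 of 10 cut-off even a free choice stays within 0.10. The excess comes mainly from the cut-off.

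Three further points stand. Whether 0.10 is actually exceeded depends on the correlation between visits, which the documents do not give. Some disagreement between tests on 10 and 15 subjects is expected and is not in itself an error. And response is a secondary endpoint: safety is primary, and no dosing or stopping rule in the protocol depends on this test.

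**Conclusion.** The point holds in a limited form. The combined 15-subject test is the planned analysis and is sound on its stated terms: type I error 0.0168 per time point, at most 0.0504 over three, power 0.849. The added 4 of 10 rule is inconsistent with the correction that section 7.1 says is included (0.0500 against 0.0333). If it were used to reject, the family-wise rate would lie between 0.050 and 0.143 across the range from identical to independent visits, with a bound of 0.150. If either rule were allowed, the bound is 0.162. Its 0.83 power overstates what ten subjects give at the corrected level, which is 0.62.

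A separate, smaller gap is that the rule has no status, so the text does not exclude using it after the responses are seen. Correcting the cut-off alone would not close that gap, because the two rules would still disagree on some datasets.

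These figures assume independent subjects and, for the joint calculations, the same response rate in both cohorts. The correction is worth making because this is the only hypothesis test in the plan with stated power and rejection rules, but it does not touch the primary safety endpoint.

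**What to change.** In section 7.1, state that the only test that can reject the 15% null is the combined 15-subject test (6 or more of 15), applied at each Bonferroni-corrected time point. Replace the 4 of 10 rule and its 0.83 power with a sentence such as: The response rate in the 10 expansion subjects will be reported with an exact confidence interval as a supportive analysis; no hypothesis test will be based on it.

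If the sponsor prefers to keep an expansion-only test, label it supportive and restate it at the corrected level: 5 or more of 10, type I error 0.0099, power 0.62.

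The change is a matter of wording and needs no further subjects or data. The power of the deciding test stays at 0.849. The small cost is that the sponsor gives up a second route to rejection.

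### Section 7.1's expansion-only rule (4 of 10, power 0.83) does not meet the Bonferroni-corrected level that the 15-subject rule meets; the cutoff that does is 5 of 10, with power 0.62

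*Combined protocol and SAP*

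**What the plan says.** Section 7.1 (Statistical Methods) sets up one exact binomial test of the GVHD response rate. The hypotheses are "a null hypothesis of a 15% response rate" and "an alternative hypothesis of a 50% response rate", at "a one-sided significance level of 0.10". Response rates at the three assessments "will be assessed using exact binomial methods combining the initial dose escalation and expansion cohorts".

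For the pooled 15 subjects the section says the test "would have a power of 85% using 15 subjects". It presents that figure as already allowing for multiplicity, in these words: "including a Bonferroni correction for looking at the 6 week, 3 month and 6 month response rates". The cutoff follows: "This test rejects the null hypothesis if 6 out of 15 subjects respond".

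The next sentence takes the 10 expansion subjects alone and says "the null is rejected if 4 out of 10 respond, and the power is reduced to 0.83". It does not change the significance level, set the correction aside or single out a time point. Section 3.3 and the Study Summary list the same three time points, and neither ranks one above the others.

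**The concern.** The two rules sit side by side as the same test at two sample sizes, and the second is described as a reduction in power from the first. A reader will take both to be at the same corrected level. If 4 of 10 does not meet that level, two things follow:

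- A prespecified threshold would allow a positive claim at an error rate the plan rules out.
- The expansion-only analysis would look like a near-equal substitute for the pooled one (0.83 against 0.85) when it is much weaker.

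The expansion-only analysis is a plausible choice at reporting. Under section 5.1.1 the first five subjects escalate through dose levels while the expansion cohort is planned at one dose schedule, and nothing says when the 10-subject analysis would be used in place of the pooled one. Its threshold therefore needs to be right in advance.

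**Working it through.** **Inputs, all from section 7.1.** Null rate p0 = 0.15; alternative p1 = 0.50; one-sided level 0.10; three time points under Bonferroni; n = 15 pooled and n = 10 expansion only; exact binomial test.

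**Per-test level.** 0.10 / 3 = 0.0333.

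**Formulas.** For a rule that rejects when at least r of n respond:
- type I error = P(X ≥ r | n, 0.15)
- power = P(X ≥ r | n, 0.50)

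The correct cutoff is the smallest r whose type I error is at or below the per-test level.

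**Results.**

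| n | r | Type I error | Power | Meets 0.10? | Meets 0.0333? |
|---|---|---|---|---|---|
| 15 | 5 | 0.0617 | 0.941 | yes | no |
| 15 | 6 | 0.0168 | 0.849 | yes | yes |
| 10 | 3 | 0.1798 | 0.945 | no | no |
| 10 | 4 | 0.04997 | 0.828 | yes | no |
| 10 | 5 | 0.0099 | 0.623 | yes | yes |

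**Reproducing the plan's figures.**
- 6 of 15 gives power 0.849, the stated 85%.
- 4 of 10 gives power 0.828, the stated 0.83. Each power is right for the cutoff printed with it.

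**Which level each cutoff fits.**
- n = 15: an uncorrected 0.10 test would reject at 5 of 15. The plan uses 6, the smallest cutoff that meets 0.0333, so this rule fits the stated correction.
- n = 10: an uncorrected 0.10 test rejects at 4 of 10, which is the plan's rule. At 0.0333 the smallest valid cutoff is 5 of 10. The Šidák level, 1 − 0.9^(1/3) = 0.0345, gives the same cutoff.

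**Familywise error of 4 of 10 used at all three time points.**
- Bonferroni bound: 3 × 0.04997 = 0.150, against 0.10 allowed.
- If the three tests were independent: 1 − (1 − 0.04997)³ = 0.143.
- The same patients are scored each time, so the results will be correlated. The documents give no value, so a range was simulated (exchangeable latent-normal responses, 100,000 replicates). The error was 0.141 at latent correlation 0, 0.128 at 0.5, 0.118 at 0.7 and 0.096 at 0.9.

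**Like-for-like cost of dropping five subjects.**
- Both rules corrected: 0.849 − 0.623 = 0.226.
- Both rules uncorrected: 0.941 − 0.828 = 0.113.
- As printed: 0.85 − 0.83 = 0.02. This compares a corrected rule with one that fits only the uncorrected level.

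**The case against.** The only level the section prints is 0.10; 0.0333 has to be derived. The Bonferroni phrase is attached to the 15-subject sentence, and the 10-subject sentence does not repeat it. On that reading 4 of 10 and 0.83 are correct uncorrected figures whose basis was left unstated. How the mismatch arose is also an inference: a per-test level of 0.05 would produce both 6 of 15 and 4 of 10.

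The reach is limited as well. Response is a secondary endpoint, safety is primary, and the pooled 15-subject test is the planned analysis. Only exactly 4 responders in 10 would change the verdict at a time point. With very high correlation between time points the actual familywise error falls below 0.10.

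Much of this stands as a limit on the consequences. It does not repair the sentence. The text continues the same test, announces no change of level, and presents the power as reduced from the corrected figure. A per-test level of 0.05 is stated nowhere, and three such tests carry a bound of 0.15. Bonferroni, the method the plan names, gives no credit for correlation. Even on the uncorrected reading, setting 0.83 beside 0.85 misleads, because the matching pooled figure would be 0.94.

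**Conclusion.** The point holds. At 0.10/3 per test, 4 of 10 is not a valid cutoff (type I error 0.0500 against 0.0333). The valid cutoff is 5 of 10, with type I error 0.0099 and power 0.62. The power overstatement is about 0.21 (0.83 against 0.62) and follows from the cutoff, so this is one error with two visible effects.

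The conclusion assumes that the correction stated for the three time points governs both sample sizes, which is how the section reads. It does not depend on why the figures differ. The inflation of the familywise error does depend on the unknown correlation: up to 0.150 by the bound, and 0.096 to 0.141 in the simulations. The pooled rule and its power are correct.

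**What to change.** Change the last rule in section 7.1 in one of two ways; the choice is the sponsor's.

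1. Keep the correction for the expansion-only analysis: reject if at least 5 of 10 respond, with power 0.62.
2. Name one time point as the tested one for the expansion-only analysis, and state that 4 of 10 and power 0.83 apply there at one-sided 0.10 without the Bonferroni correction. In that case do not describe 0.83 as a reduction from 0.85, since the two are at different levels; the uncorrected pooled figure is 5 of 15 with power 0.94.

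Either way, the per-test level should be printed and the section should say when the 10-subject analysis would be used.

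The cost is one or two sentences, settled before the response data are analysed. No patients, visits or procedures are added. Under the first option the stated power becomes less favourable; under the second, the expansion-only claim is confined to one time point.

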## 7.2 Subject Population(s) for Analysis

Any subject withdrawing from the study prematurely due to toxicity will be evaluable for toxicity and will not be replaced. Subjects withdrawing from the study for reasons other than toxicity (eg, due to relapse of malignancy) will be replaced. All subjects remaining on the study for at least 6 weeks will be evaluable for efficacy.

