## **4.4 Early Withdrawal of Subjects**

### **4.4.1 When and How to Withdraw Subjects**

A subject may choose to not be in this study at any time. Leaving the study will not affect regular medical care in any way. Participants will be asked to contact study staff if they are thinking about leaving the study. In addition, a follow-up visit will be utilized to ensure the safety of any participant who chooses to discontinue enrollment on this study. Any subject withdrawing from the study prematurely due to toxicity will be evaluable for toxicity and will not be replaced. Subjects withdrawing from the study for reasons other than toxicity (eg, due to relapse of malignancy) will be replaced. All subjects remaining on the study for at least 6 weeks will be evaluable for efficacy.

Any protocol physician may stop the study at any time. In addition, participants may be asked to leave the study. Possible reasons to terminate participation may include:

1. Serious side effect ( $\geq$  grade 4 adverse event)
2. Inability to tolerate dose of medication.
3. No longer meeting criteria for this study.
4. Development of new conditions needing other treatments.
5. Emergence of new therapy or studies.
6. Progression of disease.
7. Personal choice of the subject to stop study participation.

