### **4.4.2 Data Collection and Follow-up for Withdrawn Subjects**

If a subject withdraws consent to participate in the study, attempts will be made to obtain permission to record data (including survival data) up to the protocol-described end of the subject's follow-up period. In such an instance, the patient will be contacted by phone.

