### **5.7 Treatment Discontinuation and Subsequent Therapy**

If there is progression of disease on evaluation at 6 weeks, 3 months or 6 months, the patient will be considered for other secondary therapies, depending on the severity of the cGVHD and his/her overall clinical status. Other commonly used secondary therapies include Tacrolimus/sirolimus, Mycophenolate mofetil, extracorporeal photophoresis (ECP), JAK1/2 inhibitors and other monoclonal antibodies. Pulsed steroid therapy may also need to be considered in an effort to control the degree of GVHD as a purely temporary measure (ie, “bridge” to secondary therapy).

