**Visit 4 at 4-6 weeks from initiation of the combination therapy (sooner as clinically indicated)**

- i. A subject will be assessed for:
  - a. Medical history
  - b. Physical examination, including height and weight
  - c. Blood and urine tests, as clinically indicated
  - d. Additional organ function, as clinically indicated
- ii. Patients will be followed at no longer than two-week intervals over the first six weeks on trial, more frequently as clinically indicated. Note: participants in the dose escalation portion of the protocol will be followed via weekly visits, more frequently as indicated.

2. Assessment

- a. **At the 6 week (+/- 3 days) follow up visit, the degree of cGvHD will be formally re-assessed, again using NIH assessment and scoring forms (Attachment 1)**
- b. **After the 6 week follow up visit, patients may be followed at 2-4 week intervals, if clinically appropriate**
- c. Subjects may undergo repeat Rituximab weekly x4 therapy at 8 weeks after the initial therapy, depending on their prior clinical response
- d. **Formal re-assessment of cGvHD response via NIH criteria (Attachment 1 forms) will again be undertaken at the 3 month (+/- 7 days) and 6 month (+/- 7 days) follow up visits, to determine updated cGvHD status**
- e. If the subject shows progression of cGvHD, alternative treatment options will be discussed, including the appropriateness for removal from the study
- f. If the subject shows improvement (at least a partial response, by NIH response criteria), he/she will be continued on Ibrutinib for maintenance
- g. After 6 months, subjects will be followed for survival only.

Subsequent visits between the 6 week post-initiation period and 6 month follow-up timeframe will be at 2-4 week intervals, more frequently if clinically indicated (as outlined above). Serum biomarkers will be drawn at the 6 week, 3 month and 6 month post-initiation visits.

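### Early leavers can fall out of the response denominator: non-toxicity leavers are replaced, efficacy evaluability starts at 6 weeks, and no all-treated efficacy set is defined

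*Combined protocol and SAP*

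**What the plan says.** Section 7.2 is the plan's only definition of analysis populations, and Section 4.4.1 repeats it. It has three parts.

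- Subjects who leave early because of toxicity are evaluable for toxicity and are not replaced.
- For everyone else: "Subjects withdrawing from the study for reasons other than toxicity (eg, due to relapse of malignancy) will be replaced". Relapse of malignancy is only an example.
- For efficacy: "All subjects remaining on the study for at least 6 weeks will be evaluable for efficacy".

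The list in 4.4.1 of possible reasons to end participation includes "Progression of disease", and nothing exempts that reason from replacement. Section 6 (Visit 4, assessment items) is softer: "If the subject shows progression of cGvHD, alternative treatment options will be discussed, including the appropriateness for removal from the study". Section 5.7 links progression to the scheduled visits: "If there is progression of disease on evaluation at 6 weeks, 3 months or 6 months". After baseline, the first formal cGVHD assessment is at 6 weeks (Sections 5.1.2 and 6).

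Section 7.1 assumes that "a total of 15 patients will be available for evaluation" and gives the decision rule: "This test rejects the null hypothesis if 6 out of 15 subjects respond". It sets a 15% null, a 50% alternative, a one-sided level of 0.10 with a Bonferroni correction over three time points, and 85% power. It does not say whether the 15% and 50% refer to treated or to evaluable subjects.

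**The concern.** Doing badly on treatment can itself be a reason to leave. If those who leave before 6 weeks are not counted, and some are replaced by subjects with a fresh chance to respond, the response rate among those counted can only be equal to or higher than the rate among those treated.

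The number analysed is also left open. Early toxicity leavers may drop out without replacement, which takes it below 15. A subject who leaves after 6 weeks for another reason is both evaluable and replaced, which takes it above 15. The exact test can be run at any n, but the plan does not say which n applies. In an open-label trial that choice could be made with the responses known.

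Response rate is secondary, but it is the only endpoint with a hypothesis, a significance level and a power figure.

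**Working it through.** **Inputs.** From 7.1: n=15, cutoff 6, null 0.15, alternative 0.50, per-look level 0.10/3 = 0.0333. The documents give no early-loss rate. I therefore assume a share f of treated subjects who leave before 6 weeks without responding and are not counted, and show f = 10% and 20%.

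**Formula.** P(X ≥ r | n, p) = Σ from j=r to n of C(n,j) p^j (1−p)^(n−j).

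**1. The plan's own figure.** P(X ≥ 6 | 15, 0.50) = 0.849, which matches the stated 85%. P(X ≥ 6 | 15, 0.15) = 0.0168, below 0.0333. The design figures reproduce.

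**2. Effect on the estimate.** Reported rate = treated-subject rate / (1−f).

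- f = 10%: 0.50/0.90 = 55.6%
- f = 20%: 0.50/0.80 = 62.5%

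**3. Effect on the conclusion** (null 0.15, level 0.0333).

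| Early losses | Counted subjects | All treated | Reversal? |
|---|---|---|---|
| 3, all replaced | 6/15, p=0.0168 | 6/18, p=0.0419 | yes |
| 3, none replaced | 5/12, p=0.0239 | 5/15, p=0.0617 | yes |
| 2, both replaced | 6/15, p=0.0168 | 6/17, p=0.0319 | no |
| 2, none replaced | 5/13, p=0.0342 | 5/15, p=0.0617 | no (neither rejects) |

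The exact cutoff is 6 for every n from 13 to 17. Three losses of which only one or two are replaced (13 counted and 16 treated, or 14 and 17) therefore do not reverse the conclusion either.

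**4. Type I error of the 6/15 rule.** If the 15% null is an all-treated rate and leavers are replaced, the rate among counted subjects is 0.15/(1−f).

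- f = 0: P(X ≥ 6 | 15, 0.150) = 0.017
- f = 10%: P(X ≥ 6 | 15, 0.1667) = 0.027
- f = 20%: P(X ≥ 6 | 15, 0.1875) = 0.046
- It equals 0.0333 at f = 0.138.

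If the 15% refers to evaluable subjects, it stays at 0.017 for every f.

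**5. Check of the remedy.** The smallest r with P(X ≥ r | n, 0.15) ≤ 0.0333 is 6 for n = 15–17, 7 for 18–21 and 8 for 22–26. Suppose enrolment continues until 15 subjects have not been replaced, so that the number replaced is negative binomial (15, 1−f). The type I error under an all-treated 15% null is then 0.0224 (f = 10%) and 0.0220 (f = 20%), both within 0.0333.

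If the 50% was meant for evaluable subjects, the treated-subject rate is 0.50 × (1−f), that is 0.45 or 0.40. Power is then:

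| | f = 10% | f = 20% |
|---|---|---|
| With replacement, averaged over the number treated | 0.81 | 0.72 |
| 15 treated, no replacement | P(X ≥ 6 given 15, 0.45) = 0.74 | P(X ≥ 6 given 15, 0.40) = 0.60 |

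**The case against.** Five objections deserve an answer.

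- **Exclusion is inferred.** Section 7.2 says who is evaluable and does not say that only they are. This stands as a limit. Exclusion is still the natural reading, and if early leavers are meant to count, the plan should say so.
- **The progression route is thin.** Formal assessment first happens at 6 weeks, and a subject found to progress at that visit will normally already be evaluable. Section 6 only has removal discussed. A reader might infer that early progressors are removed and replaced by design. The documents do not support that: early exit for progression is possible under 4.4.1, but it is not scheduled. Relapse of malignancy, the one example given, is a competing event and not a failure of cGVHD treatment, so counting such leavers as non-responders is a choice.
- **Late leavers.** A reader might carry the 6/15 against 6/18 contrast over to 3 and 6 months by leaving out subjects who withdraw after 6 weeks. That contradicts 7.2, under which they remain evaluable. The gap for them is narrower: how a missing 3- or 6-month assessment is scored, and whether both they and their replacements count.
- **The reversals are selected cases.** This is correct. They need three early losses, all replaced or none replaced, and exactly the borderline number of responders.
- **Replacement is ordinary in a small phase 1/2 study with a safety primary endpoint.** Also correct, and it limits the severity. Replacement is not the defect. The defect is that the only powered test has no all-treated denominator.

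Section 4.4.2 does not close the gap. Its statement that "attempts will be made to obtain permission to record data" covers only subjects who withdraw consent, with contact by phone, and says nothing about how they are counted.

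**Conclusion.** The point holds in conditional form and should be fixed. On the natural reading of 4.4.1 and 7.2, early leavers without a response drop out of the denominator, and the reported rate can overstate the rate in treated subjects by a factor of 1/(1−f): 1.11 at 10% early loss and 1.25 at 20%. Both loss rates are assumptions.

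The choice of denominator can change the conclusion only in the borderline cases shown. A reader might infer that the false-positive rate is inflated as the plan stands. The documents do not establish this: 0.0333 is exceeded only above about 14% early loss, and only if the 15% null is an all-treated rate, which 7.1 leaves open. The primary safety endpoint is not affected.

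**What to change.** In 7.2, write along these lines:

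- The main efficacy set is all subjects who receive at least one dose of study treatment, at 6 weeks, 3 months and 6 months.
- A subject with no response assessment at a time point, because of withdrawal for any reason, death or a missed visit, counts as a non-responder at that time point.
- A treated subject who is replaced stays in the denominator.
- The exact binomial cutoff for the actual number treated applies: 6 for 15–17, 7 for 18–21, 8 for 22–26.
- Sensitivity analyses: the 6-week-evaluable rate, and the rate with withdrawals for relapse of malignancy excluded.

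State in 7.1 that the 15% and 50% rates refer to this set, and make 4.4.1 match. The change concerns counting only and alters no treatment or withdrawal decision.

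**Cost.** Wording in three sections and no new assessments. The reported rate will be lower wherever there are early losses. If the 50% was meant for evaluable subjects, power falls from the stated 0.85 to the values in the last table of the working, and the sponsor should decide whether that is acceptable.
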